8.2 Assessment of Efficacy

All the study endpoints for the clinical trial will be compared between the IMP and the placebo groups at study end-point (visit 3/ day 182), adjusting for the baseline.

8.2.1 Primary Efficacy Parameters

Our primary efficacy parameter will be measured using the Comprehensive Assessment of At-Risk Mental States' (CAARMS)¹ (Monthly Version 2006). This is a validated instrument to rule out or confirm criteria for acute psychosis, map a range of psychopathology and functioning factors over time in young people at ultra high-risk of psychosis, and determine if an individual meets the criteria for an 'At Risk Mental State'. We will be using the English version in this population. The assessment has 7 subscales that target different areas of psychopathology and functioning: 1. Positive symptoms, 2. Cognitive change attention/concentration, 3. Emotional disturbance, 4. Negative symptoms, 5. Behavioural change, 6. Motor/physical changes, and 7. General psychopathology. Each subscale item is scored against (i) Severity (from 0 -never, absent – to 6 – extreme/psychotic/psychotic and severe –. Most items are also scored against (ii) Frequency and duration (from 0 – absent – to 6 – continuous) and (iii) Pattern of symptoms (from 0 – no relation to substance use noted – to 2 – noted only in relation to substance use). Moreover, a few items are additionally scored against (iv) Level of distress (from 0 to 100). Finally, the CAARMS includes: 8. Inclusion criteria for Group 1 Vulnerability group, Group 2 Attenuated psychosis group (CHR-APS), and Group 3 BLIPS group; 9. Psychosis threshold criterion (based on symptom severity, frequency,

and duration); and 10. Study withdrawal threshold criterion (based on Aggression/Dangerous Behaviour and/or Suicidality/Self Harm subscale severity) (Appendix 1). Within this instrument, lower scores are indicative of improved state, and higher scores of worsened state.

Primary clinical outcome: Severity of psychotic symptoms as measured using the CAARMS subscale Positive symptoms ¹. This subscale includes 4 items: 1. Unusual thought content, 2. Non-bizarre ideas, 3. Perceptual abnormalities, 4. Disorganised speech. Each subscale item is scored against (i) Severity (from 0 – never, absent – to 6 – psychotic/psychotic and severe –, (ii) Frequency and duration (from 0 – absent – to 6 – continuous), (iii) Pattern of symptoms (from 0 – no relation to substance use noted – to 2 – noted only in relation to substance use), and (iv) Level of distress (from 0 to 100). Within this instrument, lower scores are indicative of improved state, and higher scores of worsened state.

8.2.2 Secondary Efficacy Parameters

Our secondary efficacy parameters will be measured using:

- The Comprehensive Assessment of At-Risk Mental States' (CAARMS) ¹(Monthly Version 2006). This is a validated instrument to rule out or confirm criteria for acute psychosis, map a range of psychopathology and functioning factors over time in young people at ultra high-risk of psychosis, and determine if an individual meets the criteria for an 'At Risk Mental State'. We will be using the English version in this population.

- The Hospital Anxiety and Depression Scale (HADS), an English self-assessment scale developed and found to be a reliable instrument for detecting states of depression and anxiety in the setting of an hospital medical outpatient clinic. The anxiety and depressive subscales are also valid measures of severity of the emotional disorder ⁶¹. Both the Anxiety and Depression scales range from 0 to 21, with 3 cut-offs: 0-7 = Normal; 8-10 = Borderline abnormal (borderline case); and 11-21 = Abnormal (case).

- The Social and Role Functioning scale ⁶², an English scale assessing participants' psychosocial functioning. Both the Social and Role scales range from 1 to 10, with 10 indicating superior functioning and 1 indicating extreme dysfunction. To increase reliability, both scales include focused and detailed anchor points for each rating interval. Each scale generates 3 scores: current functioning which is the lowest level of functioning in the past month, lowest and highest level of functioning reported over the past year.

Secondary clinical outcomes:

1) Distress associated with psychotic symptoms as measured using the CAARMS¹ subscale Positive symptoms – Level of distress score

2) Severity of anxiety symptoms assessed using the Hospital Anxiety and Depression Scale (HADS) ⁶¹ and level of psychosocial functioning assessed using the Social and Role Functioning scale⁶²

3) Clinical remission, as defined as no longer meeting the criteria for a diagnosis of CHR-APS

4) Total CAARMS score assessing psychopathology and functioning across all 7 CAARMS subscales

5) Change (study endpoint minus baseline) in the severity of psychotic symptoms as measured using the CAARMS between the CBD and placebo groups

8.3 Procedures for Assessing Efficacy Parameters

Efficacy parameters will be assessed through clinical interview using standardized questionnaires/ rating instruments

8.3.1. Clinical Outcome assessment:

CAARMS psychotic symptom severity will be operationalised as in the study by Morrison and colleagues ¹² by summing the scores of product of the global rating and frequency scores of the four items of the CAARMS subscale Positive symptoms¹. CAARMS ratings will be carried out by a clinical researcher appropriately trained in administering CAARMS.

Distress associated with psychotic symptoms will be assessed by summing the Level of distress scores of the the four items of the CAARMS subscale Positive symptoms¹. Anxiety symptoms will be assessed using the Hospital Anxiety and Depression Scale (HADS) ⁶¹ Anxiety scale score.

Level of global functioning will be assessed using the Social and Role Functioning scale current functioning score ⁶².

*Clinical remission* will be defined on the basis of the CAARMS criteria ¹ as in previous studies ⁷¹. Remission requires a score of < 3 on the 'unusual thought content', 'non-bizarre ideas' and 'perceptual abnormalities' subscales and < 4 on the 'disorganized speech' subscale and a frequency scale score of < 3 over the past month.

Total CAARMS score will be operationalised by summing the scores of product of the global rating and frequency scores of all the CAARMS subscales.

In case of missing data, we will get back to the relevant study site in order to complete it.

8.4 Assessment of Safety

8.4.1 Specification, Timing and Recording of Safety Parameters

At screening the main safety measures will involve checking for study inclusion/ exclusion criteria, physical examination/ medical history/ safety blood investigations to ensure the absence of relevant disease or conditions that are a contraindication to participation in the study procedure as relevant. These will be repeated at Visit 3 or at withdrawal. Urine pregnancy test will be carried out at each visit for female participants. In the event of a positive test, the patient will be withdrawn from the study and their GP and mental health team informed. These are summarised in detail per visit below.

Screening Visit (Visit window -1): Medical History, Physical Examination (Vital signs, ECG), Pregnancy test (as appropriate), Clinical laboratory (Haematology: Full blood count and Haemoglobin; and Biochemistry: Urea & Electrolytes, liver function test, lipid profile).

Baseline Visit (Randomisation, on Day 0): Physical Examination (Vital signs, ECG), Pregnancy test (as appropriate), UKU Side-effect rating scale.

Month One Visit (Visit Window 1, at approximately Day 28): Pregnancy test (as

appropriate), AEs, UKU Side-effect rating scale.

Month Three Visit (Visit window 2, at approximately Day 91): Pregnancy test (as appropriate), AEs, UKU Side-effect rating scale.

Month Six Visit (Visit window 3, at approxiamtely Day 182): Physical Examination (Vital signs, ECG), Pregnancy test (as appropriate), Clinical laboratory (Haematology: Full blood count and Haemoglobin; and Biochemistry: Urea & Electrolytes, liver function test, lipid profile), AEs, UKU Side-effect rating scale.

Month Seven Final safety visit (Visit window 4, at approaximately Day 212): AEs/SAEs. This is going to be the final study visit.

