4.3 Trial Flowchart

Outcome	Screening	0	1	2	3	4
Week No.	-1 to -3	1	4	13	26	30
			(±3day)	(±7days)	(±14days)	(±7days)
Informed Consent	X					
Socio-demographic	X					
Information						
Medical History	X					
Physical examination	X	Х			Х	
(Vital Signs, ECG)						
Urine Drug Abuse		Х	Х			
Screen						

AUDIT, FTND, CEQ, SDS	X				X	
TFLB		X	X		X	
Cannabinoid levels in blood to confirm use of or abstinence from cannabis		X	X	X	X	
Pregnancy Test	Х	Х	Х	X	X	
Screening Blood Sampling- Clinical laboratory (Haematology & Biochemistry)	X				X	
Concomitant	Х	Х	X	X	X	
Medication						
Study Exclusion criteria check	X	X				
NART	Х					
Adverse Events		Х	X	X	X	X
Randomisation		Х				
Study Medication Dispensing		X	X	X		
Study Medication Compliance (pill count)			X	X	X	
Compliance Blood Sampling (Cannabidiol levels)		X	X	X	X	
Comprehensive Assessment of At-Risk Mental State	X	X	X	X	X	
Hospital Anxiety Depression Scale		X	X	X	X	
Global Functioning (Social and Role scales)		X			X	
UKU Side Effect Rating Scale		X	X	X	X	

5 Participants

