6.1.3 Dosing Regimen

For both the internal pilot and the RCT, the trial medication (CBD 600mg/day in capsule or matching placebo capsules) is to be taken once a day, after the first meal of the day, for a maximum of 182 days.

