7.2 Baseline Visit (Randomisation, on Day 0): Following satisfactory completion of screening, patients will be randomised to one of the treatment arms in a double-blind manner. Before randomisation baseline measures (CAARMS and HADS including alcohol and drug use (in particular cannabis)⁶⁸⁻⁷⁰), physical examination and blood samples for cannabinoid levels and for Cannabidiol will be acquired. The participant will be randomised and study drugs dispensed from the local hub pharmacy. Side effects will also be assessed, by using the UKU side-effect rating scale ⁶³.

7.3 Month One Visit (Visit window 1, at approximately day 28): This visit will involve only clinical assessments, assessment of alcohol and drug use (in particular cannabis), blood sampling, monitoring of compliance, side effects, AEs, and dispensing of study drugs.

7.4 Month three Visit (Visit window 2, at approximately Day 91) and Month Six Visit (Visit window 3, at approximately Day 182): These visits will involve only clinical assessments, assessment of alcohol and drug use (in particular cannabis), blood sampling, monitoring of compliance and side effects as well as AEs. Study drugs will be dispensed as well on visit 3.

7.5 Month Seven Final safety visit (Visit window 4, at approximately Day 212): Only AEs will be recorded at this visit, via review of medical records.

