7.6 Laboratory Tests

Clinical Laboratory measures: Bloods for Haematology (Full blood count and Haemoglobin) and Biochemistry (Urea & Electrolytes, liver function test, lipid profile). All blood tests will be carried out at each study site as per their standard procedure. Blood results will be printed and filed as source in the patient SDW.

Genotyping and cannabinoid measures: Blood samples for these measures will be carried out at each study site and shipped to the London site where they will be stored and analysed. Genomic and proteomic samples will be stored for use in future ethically approved research.

8 Outcomes

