Participants will be asked the open question "Have you had any health problems since you were last asked?" to evoke spontaneous reports of side-effects. Spontaneous and self-rated side-effects will be evaluated for intensity and seriousness. Deterioration in lab or examination safety measures will be recorded as AE if they are associated with symptoms or signs or if they are sufficiently marked to be clinically significant. Suicidal thoughts, acts or events are AEs that will be rated and recorded. All such events will be notified to the clinical team and carefully monitored by them. Worsening symptoms of the primary study condition will not be recorded as an AE. However, if hospitalization results from worsening of the primary study condition, the hospitalization will be reported as an SAE. Diagnoses will be recorded rather than symptoms, signs or lab parameters.

Reporting and follow-up of adverse events

All SAEs have to be reported, whether or not considered causally related to the trial medication. All SAEs will be recorded in the source data worksheet (SDW). If any SAE occurs in the course of the study, then investigators or other site personnel will inform the local Principal Investigator and clinician for that patient immediately; i.e. within one business day... All completed SAE forms will be filed appropriately in the Investigator Site File (ISF) and as required within the SDW Study Folder. The participant will be followed up by the medic until the event or reaction has reached an outcome. The participant's GP will be contacted by the PI or delegate, if it is medically indicated to do

SO.

Reporting Responsibilities

King's College London and the South London & Maudsley NHS Foundation trust have delegated the delivery of the Sponsor's responsibility for Pharmacovigilance (as defined in Regulation 5 of the Medicines for Human Use (Clinical Trials) Regulations 2004 to the King's Health Partners Clinical Trials Office (KHP-CTO).

All SAEs, SARs and SUSARs (excepting those specified in this protocol as not requiring reporting) will be reported immediately (and certainly no later than 24hrs) by the Investigator to the KHP-CTO and CI for review in accordance with the current Pharmacovigilance Policy.

The KHP-CTO will report SUSARs to the regulatory authorities (MHRA, competent authorities of other EEA (European Economic Area) states in which the trial is taking place.

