8.4.2.2 Anticipated Adverse events

In this population of CHR-APS, we anticipate:

1. AEs not related to the study intervention, not needing reporting:

- Worsening of psychotic symptoms, sleep disturbances, appetite disturbances, anxiety symptoms, mood symptoms, and suicidal ideation

- Transition to FEP

2. AEs potentially related to the study intervention, needing reporting:

- Hepatic Disorders (elevations of liver transaminases)

- Gastrointestinal Disorders (diarrhoea, gastroenteritis, abdominal pain, discomfort, weight decreased)

- Nervous System Disorders (somnolence, sedation, lethargy, fatigue, malaise, asthenia, drooling, salivary hypersecretion, gait disturbance)

- Infections (viral infections, pneumonia, fungal infections)

- Hypersensitivity Reactions (pruritus, erythema, rash, angioedema, hypoxia, respiratory failure)

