12.9.4 Interim Analysis

No interim analysis is planned. The Data Monitoring & Ethics Committee will have

access to subgroup unblind safety data on an ongoing basis and will act in accordance with the Data Monitoring & Ethics Committee charter.

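### The only scheduled on-treatment liver test for a continuing patient falls at day 182, too late to change dosing, although raised transaminases are listed as a possible drug effect

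*Protocol*

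**What the plan says.** **Liver tests.** Section 8.4.1 lists clinical laboratory tests, liver function included, at screening, and then "These will be repeated at Visit 3 or at withdrawal". Its visit-by-visit list has the laboratory panel at screening and month six, and none at day 0, day 28 or day 91. The flowchart in 4.3 agrees: haematology and biochemistry are marked at screening and visit 3 only. Section 7.6 names the liver function test but adds no time point. The day-212 contact (7.5) is a records review for adverse events, with no bloods.

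**Dosing.** Study drug is taken once daily "for a maximum of 182 days" (6.1.3). Visit 3 is week 26, that is day 182, with a window of 14 days either side (4.3).

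**The named risk.** In 8.4.2.2, the list of events that may be caused by study drug and have to be reported opens with "Hepatic Disorders (elevations of liver transaminases".

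**Blood already drawn.** The flowchart marks "Compliance Blood Sampling (Cannabidiol levels" and cannabinoid levels at visits 1 and 2. Section 7.3 gives the month-one visit as including "blood sampling, monitoring of compliance, side effects, AEs, and dispensing of study drugs". For the laboratory work, 7.6 says "All blood tests will be carried out at each study site as per their standard procedure".

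**Recording and oversight.** Under 8.4.2, "Deterioration in lab or examination safety measures will be recorded as AE", on condition that it comes with symptoms or signs or is marked enough to matter clinically. Under 12.9.4 the DMC has "access to subgroup unblind safety data on an ongoing basis".

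**The concern.** The protocol names raised transaminases as a possible effect of study drug, yet for a patient who stays in the trial it schedules no liver test while a result could still alter treatment. An enzyme rise can be free of symptoms. The open adverse-event question and the UKU scale would then not reveal it, and nothing in the schedule would prompt a blood test.

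Two things are at stake. The first is the safety of the individual patient: a clinically significant rise found at day 182 comes when dosing is over or nearly so, and one that has settled by then is never seen. The second is monitoring: the DMC is to see safety data as they accrue, but for patients currently on drug there are no scheduled liver results to show it. Scheduled liver data reach it only from patients who have got to visit 3 or withdrawn.

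**Working it through.** **Inputs**
- Screening: 1 to 3 weeks (7 to 21 days) before day 0 (7.1).
- Visit 1: day 28, window 3 days. Visit 2: day 91, window 7 days. Visit 3: week 26, window 14 days (4.3).
- Maximum dosing: 182 days (6.1.3).
- Recruitment at full rate: 28 randomised per quarter (10.2.2), 1:1 allocation (4.2).

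**1. Test date against the end of dosing.** Week 26 is 26 × 7 = 182 days, equal to the dosing maximum. Dosing days left after the visit-3 test: 182 − 182 = 0 as planned. At the early edge of the window (day 168) it is 182 − 168 = 14 days, or 14/182 = 8%. Scheduled liver tests between day 0 and the visit-3 window: none.

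**2. Gap between the two planned tests.**
- As planned: 7 + 182 = 189 to 21 + 182 = 203 days.
- With the window: 7 + 168 = 175 to 21 + 196 = 217 days.

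**3. Patients on treatment without an on-drug result.** At a steady rate of 28 per 91 days, ignoring early stops:
- Now: (28/91) × 182 = 56 patients, about 28 on CBD. If every visit 3 fell at day 168: (28/91) × 168 = 51.7.
- With a day-28 test: (28/91) × 28 = 8.6, so about 9 patients, of whom about 4 on CBD.

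**4. What an earlier test leaves open.**

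| Test | Dosing days left | Share of 182 |
|---|---|---|
| Day 28 (25 to 31) | 151 to 157 | 83 to 86% |
| Day 91 (84 to 98) | 84 to 98 | 46 to 54% |
| Visit 3 (current) | 0 to 14 | 0 to 8% |

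With both tests added, the planned gaps are 7 + 28 = 35 to 21 + 28 = 49 days, then 91 − 28 = 63, then 182 − 91 = 91. The longest planned gap falls from 189–203 days to 91.

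**5. A limit on step 3 for the DMC.** Section 12.5 has a data extract requested 6 to 8 weeks before a DMC report. If the report rests on that extract, a patient's day-28 result is in it only if randomisation was at least 28 + 42 = 70 to 28 + 56 = 84 days before the report. Patients without a result would then number (28/91) × 70 = 21.5 to (28/91) × 84 = 25.8 out of 56. That is more than 9, but still under half. The protocol does not say that the report uses this extract.

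**What cannot be sized.** The protocol gives no rate, time of onset or duration for enzyme rises, so the number that would be missed cannot be calculated.

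**The case against.** The schedule is stated consistently, so this is a design choice and not a contradiction. Section 6.2 sends drug risks to the investigator's brochure, which is not at hand and may support testing only at the end. Section 3.2.2 also reports that doses up to 1500 mg a day are well tolerated. These points limit the weight of the concern. They do not remove it: the protocol itself names the hepatic risk and gives no reason for leaving the treatment period untested, and the physiological effects that 3.2.2 goes through do not include liver values.

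Other safeguards exist and count. Adverse events are reviewed at days 28, 91, 182 and 212. The investigator can withdraw a patient for an adverse event (6.7.2). Nothing bars an unscheduled test when symptoms suggest one, and bloods are repeated at withdrawal. The trial manager is unblinded so that safety information can go quickly from sites to the DMC chair (11.2.2).

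Three stronger readings are tempting, and the protocol does not support them.
- *A hepatic problem could not be acted on at all.* It could, if it caused symptoms. The gap is in scheduled detection of symptom-free rises. Even there, 8.4.2 makes a laboratory change an adverse event only if it is symptomatic or clinically significant, so a mild passing rise would go unrecorded even if tested.
- *The tolerability question (Objective 3) cannot be answered.* The safety endpoint in 4.1.4 is the incidence of adverse effects on the UKU scale, which is completed at days 0, 28, 91 and 182. No liver-value endpoint is defined.
- *The month-12 decision is taken without liver data.* All the criteria in 8.1 concern feasibility, and none uses safety data.

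Section 7.4 says drug is dispensed at visit 3, which might suggest later dosing. The flowchart dispenses at visits 0, 1 and 2 only, and the 182-day limit stands.

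**Conclusion.** The point holds as a gap in scheduled safety monitoring that is cheap to close. For a patient who stays in the trial, the only planned liver test after starting drug comes with at most 14 of 182 dosing days left. A symptom-free but clinically significant rise has no scheduled route to detection in time to change dosing, and the DMC has no scheduled liver data from patients still on drug.

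The planned gap between tests is 189 to 203 days (175 to 217 with the visit window). About 56 patients, 28 of them on CBD, are on treatment at any time without a scheduled on-drug result, against about 9 with a day-28 test. The patient counts assume steady recruitment at 28 per quarter, no early stopping, and results available on the day of the draw. The dates and gaps rest only on the visit schedule. No claim is made about how often a rise would occur.

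**What to change.** In 4.3 and 8.4.1, add liver function tests at days 28 and 91:
- Take an extra tube at the existing blood draws and run it at the local laboratory. The drug-level samples cannot serve, because 15.2.1 has them stored and shipped to London.
- Send results to a site physician who does not rate the CAARMS.
- Include them in the DMC safety data.
- State a rule for repeat testing and for stopping drug. Without it the results cannot guide dosing consistently.

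If the brochure supports no testing before day 182, say so in 8.4.1 and confine any hepatic statement to status at day 182 or withdrawal.

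**Cost:** at most 2 × 300 = 600 extra panels, with no new visit. Some incidental findings will need follow-up. A raised result could hint at allocation, a small unblinding risk, which is why it should not reach the CAARMS rater.

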6.7.2 Withdrawal from study intervention

Category of withdrawal II: Participants may be withdrawn by the investigator for various reasons including but not limited to the following: protocol violations, inter-current illness, AEs, SAE's, SUSAR's, administrative reasons or other reasons or participation in the RCT affecting their ongoing care. Participants may also be withdrawn by the investigator in case of emergence or worsening of depression, suicidal thoughts or behaviour, or any unusual changes in mood or behaviour, suggesting serious risk to the patient. Patients will be followed up with the same schedule of research assessments as those who continue in the study, till they complete the 6-month follow-up period or till they progress to frank psychosis (whichever is earlier);

Category of withdrawal III: In case of CHR patients experiencing progression to a first episode of psychosis (frank psychosis), they will exit from the study intervention, be deemed as treatment failure, and will only be assessed for safety outcomes after confirming progression to psychosis. In line with established practice, and as used in previous clinical trials in CHR patients ^{12,14} transition to psychosis will be operationally defined using CAARMS ¹. We will carry out complete follow-up of patients who develop frank psychosis during the follow-up period.

Participants who stop treatment early will not be replaced. As an excessive rate of withdrawals can render the study un-interpretable, attempts will be made avoid unnecessary withdrawal of patients.

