6.9 Concomitant Medication

Based on participants' clinical history, concomitant requirement of psychotropic medication is an exclusion criterion for the study. Patients requiring continued treatment with psychotropic medications other than antipsychotic, antidepressant or mood-stabilizer medications during the treatment phase may be withdrawn from the study by the Chief Investigator. Very short-term treatment with rescue medications that have a sedative or calming effect (such as Benzodiazepines) during the study may be allowed. For management of concomitant therapies, please refer to the Investigators Brochure. There is a possibility of pharmacological interactions between CBD and other concomitantly administered drugs as mentioned in the investigator brochure. Throughout the study, investigators may prescribe any other concomitant medications or treatments deemed necessary to provide adequate supportive care. A complete listing of all concomitant medication received during the treatment phase will be recorded in the relevant SDW.

7 Visit assessments

For both the internal pilot and the RCT, the following visit assessments will be performed:

7.1 Screening Visit (Visit window -1): This will take place between one to three weeks prior to the baseline visit. At screening, informed consent will be obtained from those who wish to take part. Consenting patients will then be screened against the study inclusion and exclusion criteria using the CAARMS ¹, and those satisfying the criteria will be recruited by employed or delegated investigators. Safety blood samples (for routine biochemistry and haematology) will be obtained and physical examination and vital signs recorded on all participants screened (i.e. including those who are screen failures/ not randomised for some reason). Also, blood samples for genotyping as well as for cannabinoid measurements will be obtained on all participants screened who consent to it. Consent will be sought to analyse screening data as well as regarding long-term follow up beyond the outcomes of the trial and also to link participants' data to routinely collected data sources such as HES and GP records.

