8.4.2 Procedures for Recording and Reporting Adverse Events

The Medicines for Human Use (Clinical Trials) Regulations 2004 and Amended Regulations 2006 gives the following definitions:

Adverse Event (AE): Any untoward medical occurrence in a subject to whom a medicinal product has been administered including occurrences which are not necessarily caused by or related to that product.

Adverse Reaction (AR): Any untoward and unintended response in a subject to an investigational medicinal product which is related to any dose administered to that subject.

Unexpected Adverse Reaction (UAR): An adverse reaction the nature and severity of which is not consistent with the information about the medicinal product in question set out in:

The Investigator's Brochure (IB) relating to the study.

Serious adverse Event (SAE), Serious Adverse Reaction (SAR) or Suspected Unexpected Serious Adverse Reaction (SUSAR): Any adverse event, adverse reaction or unexpected adverse reaction, respectively, that

> Results in death; Is life-threatening; Required hospitalisation or prolongation of existing hospitalisation; Results in persistent or significant disability or incapacity; Consists of a congenital anomaly or birth defect.

Important Medical Events (IME) & Pregnancy

Events that may not be immediately life-threatening or result in death or hospitalisation but may jeopardise the patient or may require intervention to prevent one of the other outcomes listed in the definition above should also be considered serious.

Although not a serious adverse event, any unplanned pregnancy will also be reported via the SAE reporting system. Women who become pregnant within the study will be followed up with evaluation of the pregnancy, foetus and child.

Time period for collection of adverse events

AEs will be recorded from the randomisation visit to the final safety visit (day 212). Any AEs that are unresolved at the follow-up visit in the study will be followed up by the

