12.1 Data collection

Assessment and collection of baseline, outcome and other trial data will be performed as reported in Visit assessments. A detailed description of study instruments is also provided in 8.2 Assessment of Efficacy and 8.3 Procedures for Assessing Efficacy Parameters, they are also included within the Appendix, alongside their scoring algorithms, and coding of missing data.

Whenever possible, follow-up data will be collected independently of study intervention discontinuation. The only occasion in which follow-up data will not be collected is described in 6.6.1 Withdrawal from study Category of withdrawal I (if a participant expresses the wish to be completely withdrawn from the study).

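### Sections 8.4.1 and 6.9 withdraw patients from the study for exits that sections 6.7.2 and 12.1 keep in follow-up

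*Protocol*

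**What the plan says.** Section 6.7 defines two kinds of exit.

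- **6.7.1, withdrawal from study (Category I).** The participant asks to leave. The team first discusses stopping treatment only and staying in follow-up. Complete withdrawal follows if the participant still wants it.
- **6.7.2, withdrawal from study intervention (Category II).** The investigator decides, on an open list: "Participants may be withdrawn by the investigator for various reasons including but not limited to the following". Assessments go on: "Patients will be followed up with the same schedule of research assessments as those who continue in the study", up to six months or frank psychosis.

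Section 12.1 names a single case in which follow-up data are not collected, citing "6.6.1 Withdrawal from study Category of withdrawal I (if a participant expresses the wish to be completely withdrawn from the study").

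Two other rules use the 6.7.1 term for exits that are not the participant's wish:

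- **8.4.1:** "Urine pregnancy test will be carried out at each visit for female participants", and then "In the event of a positive test, the patient will be withdrawn from the study and their GP and mental health team informed". This is mandatory.
- **6.9:** patients who need continued treatment with psychotropics "other than antipsychotic, antidepressant or mood-stabilizer medications during the treatment phase may be withdrawn from the study by the Chief Investigator". This is discretionary.

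Neither rule refers to 6.7.2 or says that research assessments continue. Section 8.4.2 adds a separate follow-up for pregnancy: "Women who become pregnant within the study will be followed up with evaluation of the pregnancy, foetus and child".

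**The concern.** These sentences tell sites whether to keep seeing a randomised patient. A site acting on a positive test will go to 8.4.1, read a mandatory instruction in the term that 6.7.1 reserves for complete withdrawal, and may close the patient's visits. The same paragraph says of the safety checks "These will be repeated at Visit 3 or at withdrawal", which fits that reading without proving it.

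The loss would be avoidable. Section 8.3 assesses efficacy by clinical interview with rating instruments, and neither pregnancy nor a new psychotropic prescription prevents that. For pregnancy, 8.4.2 keeps the woman in contact with the trial anyway.

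Day 182 is where all efficacy endpoints are compared. In the flowchart, Social and Role Functioning has no other post-baseline measurement. Remission is analysed by logistic regression (12.9.5.2), so an earlier visit does not stand in for a missing day-182 value.

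Pregnancy is not a marker of psychotic severity. Loss related to severity is plausible only for part of the 6.9 group.

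**Working it through.** **1. The rules side by side**

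| Section | Who or what triggers the exit | Exit named | Research follow-up |
|---|---|---|---|
| 6.7.1 | Participant's wish | Study | Ends if the participant insists |
| 6.7.2, Category II | Investigator, open list | Intervention | Same schedule to 6 months or frank psychosis |
| 12.1 | – | – | Stops only for Category I |
| 8.4.1 | Positive pregnancy test | Study | Not stated |
| 6.9 | Chief Investigator, continuing psychotropic | Study | Not stated |

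By trigger, the last two rows belong with 6.7.2. By the term used, they belong with 6.7.1. Both readings cannot hold.

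**2. What the literal reading would lose**

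Inputs from the section 4.3 flowchart and section 7: post-baseline CAARMS visits at days 28, 91 and 182, so 3 visits; scheduled pregnancy tests after randomisation at the same three visits. Positive tests at screening or baseline are entry exclusions under 5.3 and are not at issue.

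Visits lost = CAARMS visits after the exit. Days lost = 182 − exit day. For pregnancy, the CAARMS of the visit with the positive test is taken as done.

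| Exit | CAARMS visits lost | Days of follow-up lost |
|---|---|---|
| Pregnancy, day 28 | 2 of 3 | 182 − 28 = 154 |
| Pregnancy, day 91 | 1 of 3 | 182 − 91 = 91 |
| Pregnancy, day 182 | 0 of 3 | 182 − 182 = 0 |
| 6.9, before day 28 | 3 of 3 | more than 154 |
| 6.9, days 28 to 91 | 2 of 3 | between 91 and 154 |
| 6.9, days 91 to 182 | 1 of 3 | up to 91 |

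Every exit before day 182 loses the primary endpoint visit. Sections 12.9.3 and 12.9.6 require at least one post-baseline measure for inclusion. Only the 6.9 exit before day 28 therefore leaves the intention-to-treat analysis. The pregnancy exits in the table do not.

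**3. Sample size, for scale only**

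The plan's figure reproduces and is not in dispute. With effect size 0.4, two-sided 0.05 and 80% power, the two-sample t-test needs 99.08 per arm, rounded up to 100. With 32% dropout, 100 / 0.68 = 147.06, rounded up to 148 per arm and 296 in total, against 300 stated.

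With 150 × 0.68 = 102 completers per arm, power is 81.1%. If 3 further patients per arm were lost beyond the dropout allowance, power would be 80.0%; with 6, it would be 78.7%. The 3 and 6 are assumptions, because the protocol gives no rate for these exits. The 32% allowance may already cover them, and this completer t-test ignores what the mixed model recovers from earlier visits. The figures are not an estimate of power lost.

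**The case against.** The best defence is that the protocol already answers the question. Neither 8.4.1 nor 6.9 says that CAARMS assessment stops. Complete withdrawal under 6.7.1 needs the participant to ask for it, 6.7.2 covers other investigator reasons through its open list, and 12.1 restricts non-collection to Category I. The word study is also used loosely. The follow-up sentence in 6.7.2 contrasts withdrawn patients with those continuing in the study, where it must mean those still on treatment. The adverse-event record in 8.4.2 and the overdose text in 11.3.2 blur the two kinds of exit as well.

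Section 12.1 is not a perfect anchor either. It opens with a qualifier about what is possible. Its claim to a single exception sits badly with Category III, under which patients with frank psychosis are assessed for safety only. Section 6.7.2 names neither pregnancy nor concomitant medication. The 6.9 rule is discretionary and narrow: it leaves out antipsychotics, antidepressants and mood stabilisers, and very short-term rescue sedatives may be allowed.

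Much of this stands. The intended rule can be inferred, so this is a conflict of wording and not an open question, and the visit losses above apply only on a literal reading. It does not remove the conflict. Section 8.4.1 is a mandatory instruction, and a site has to reconcile three other sections to learn that it does not mean what it says.

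**Conclusion.** The concern holds, at minor severity. Sections 8.4.1 and 6.9 apply the term for complete withdrawal to exits that 6.7.2 and 12.1 keep in follow-up. Section 8.4.1 is the stronger case because it is mandatory; 6.9 is secondary.

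This rests on reading pregnancy and continuing psychotropic use as falling under the open list in 6.7.2, and on sites possibly acting on the literal wording. Under that reading the cost per patient is definite: the day-182 visit is lost for any exit before day 182. How many patients would be affected is unknown and probably small, and no bias is estimated.

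**What to change.** In 8.4.1, for tests after randomisation only, and in 6.9, change the exit to withdrawal from study intervention (Category II, 6.7.2). State in both places that research assessments continue to day 182 and safety follow-up to day 212 unless the participant declines. Keep positive tests at screening and baseline as entry exclusions, and leave the frank-psychosis rule in 6.7.2 as it is. When the text is opened, correct the pointer in 12.1 from 6.6.1 to 6.7.1; this is clerical, since the category named there already makes the target clear.

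The cost is a change of wording in two sections and one cross-reference. Any extra visits are ones that 6.7.2 and 12.1 already promise.
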